9.1 Definitions

Adverse Event

An adverse event is any untoward medical occurrence associated with the use of a drug in humans, whether or not considered drug related. It can be any unfavorable and unintended sign (e.g., an abnormal laboratory finding), symptom, or disease, temporally associated with the use of a drug.

AE Grading Criteria:

The study site will grade the severity of adverse events experienced by study participants on a scale from 1 to 5 according to NCI CTCAE v4.03 or current version. Grade 1 and grade 2 adverse events do not require reporting. Adverse events not included in the NCI CTCAE should be recorded and graded according to the General Grade Definition provided below:

ADVERSE EVENT GENERAL GRADE DEFINITIONS

Grade 1	Mild	Asymptomatic or mild symptoms; clinical or diagnostic observations only; intervention not indicated
Grade 2	Moderate	Minimal, local or non-invasive intervention indicated; limiting age-appropriate instrumental ADL*
Grade 3	Severe	Severe or medically significant, but not immediately life-threatening; hospitalization or prolongation of hospitalization indicated; disabling; limiting self-care ADL**
Grade 4	Life-threatening	Life-threatening consequences; urgent intervention indicated
Grade 5	Death related to AE	Death related to AE

*Instrumental ADL: Preparing meals, shopping for groceries or clothes, using the telephone, managing money, etc.

Carfilzomib for Treatment of cGVHD

**Self-care ADL: Bathing, dressing and undressing, feeding self, using the toilet, taking medications, and not bedridden.

Suspected Adverse Reactions – a subset of Adverse Events based on causality

A suspected adverse reaction is any adverse event for which there is a *reasonable possibility* that the drug caused the event. *Reasonable possibility* means there is evidence to suggest a causal relationship between the drug and the event. Some examples are:

- A single occurrence of an event that is uncommon and known to be strongly associated with drug exposure.
- One or more occurrences of an event that is not commonly associated with drug exposure, but is otherwise uncommon in the population exposed to the drug. If the event occurs in association with other factors strongly suggesting causation (e.g., strong temporal association, event recurs on re-challenge), a single case may be sufficiently persuasive. Often, more than one occurrence is needed before the sponsor-investigator can determine that there is a reasonable possibility that the drug caused the event.
- An aggregate analysis of events observed in a clinical trial that indicates those events occur more frequently in the drug treatment group than in a similar population not receiving the study drug.

If there is reason to conclude with certainty that the drug caused the event, the event is classified as an **Adverse Reaction**.

Unexpected

An adverse event is considered unexpected *if it is not listed in the investigator brochure, or is not listed at the specificity or severity that has been observed in the event*. “Unexpected” also refers to adverse events that are mentioned in the investigator brochure as occurring with a class of drugs or as anticipated from the pharmacological properties of the drug, but are not specifically mentioned as occurring with the particular drug under investigation.

Serious

An adverse event is considered “serious” if, in the view of either the investigator or the sponsor, it results in any of the following outcomes:

1. Death
2. A life-threatening adverse event (places the subject at an immediate risk of death)
3. Inpatient hospitalization or prolongation of existing hospitalization

4. A persistent or significant disability or incapacitation
5. A congenital anomaly or birth defect

Additionally, events that jeopardize the subject and may require medical or surgical intervention to prevent one of the outcomes above may also be considered serious based on appropriate medical judgment.

9.2 Recording of Adverse Events

The study will collect all Grade 3 and above adverse events, regardless of relationship to study therapy or study procedures. Severity grading will be based on the current version of the Common Terminology Criteria for Adverse Events (CTCAE). Grade 1 and 2 events will not be collected.

Adverse events will be collected from the time of first study procedure or first dose of carfilzomib until 30 days after the last dose of carfilzomib. Events that occur after this time will be recorded only if there is a reasonable possibility that the event was caused by a study procedure or carfilzomib. All recordable adverse events will be followed until resolution.

Reporting procedures:

All Grade 3 and above adverse events will be reported through case report forms and must be recorded in the database within 7 calendar days of becoming aware of the event. All AEs are documented and reported as applicable from the time of ICF signature through 30 days after the last dose of study drug.

Exceptions:

The following are frequent events in the chronic GVHD population and will not be recorded as adverse events *as long as they are not serious*:

- Abnormalities present at study enrollment: Will not be considered adverse events, unless such abnormalities worsen (i.e. increase in frequency, intensity, or present new complications or untoward events) during study follow up
- Electrolyte abnormalities: Increase or decrease in sodium, potassium, chloride, bicarbonate, phosphorus, magnesium, calcium, hyperglycemia following steroid therapy
- Ocular: GVHD related eye dryness, discomfort, requirement for moisturizing eye drops or other topical GVHD ocular therapies or interventions (e.g. punctal plugs, scleral lenses), changes in visual acuity.

Carfilzomib for Treatment of cGVHD

- Dermatology: Nail changes, GVHD rash (to include erythema, scleroderma, ulceration, lichenoid changes, hyper- or hypo-pigmentation, dry skin and alopecia) or cushingoid appearance due to steroid therapy.
- Gastrointestinal: Xerostomia, oral ulcers or other GVHD associated lesions, oral pain or sensitivity, anorexia, difficulty swallowing due to esophageal stricture or narrowing, nausea/vomiting, salivary gland changes, GVHD associated abdominal pain, bloating, diarrhea, weight loss
- Respiratory: shortness of breath, cough, or oxygen requirement associated with pulmonary chronic GVHD involvement
- Growth and Development: Reduced growth velocity, delayed puberty.
- Musculoskeletal changes: Avascular necrosis, fracture, arthritis, osteoporosis, decrease in range of motion associated with joint or fascial GVHD involvement
- Sexual Function: Erectile dysfunction, infertility, amenorrhea, vaginal stenosis, vaginal dryness or discomfort.
- Events secondary to routine procedures performed for chronic GVHD therapies: Extracorporeal photopheresis, PUVA therapy.

Non-serious adverse events collected in the database will be compiled by the coordinating center and reported to the DSMB approximately every 6 months.

All serious adverse events must be reported in the database within 24 hours of becoming aware of the event. Significant and relevant follow-up information should also be reported immediately within 24 hours of awareness.

Exception:

- Hospitalization for elective treatment of a pre-existing condition that did not worsen from baseline is not considered an SAE.

The site Principal Investigator must notify the coordinating center and sponsor-investigator when a serious adverse event has been entered. The sponsor-investigator will then determine whether the event meets the criteria for expedited reporting (see below) and will work with the coordinating center to prepare the IND Safety Report.

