Congestive heart failure	Clinical evidence of CHF AND either LVEF < 40% or reduction in LVEF below 55% with a drop in LVEF from	Hold CFZ	Control of clinical CHF, and return of LVEF to ≥ 40% or (if held due to drop below LVEF of 55% with > 20%	Resume CFZ at one dose decrement

Carfilzomib for Treatment of cGVHD

	prior baseline by > 20%		drop from baseline) return of LVEF to within 15% of baseline value If improvement defined above is not met	
				Discontinue CFZ therapy
Other non-hematologic toxicity \geq Grade 3	Other non-hematologic CFZ-related \geq Grade 3 toxicity not listed individually elsewhere	Hold CFZ	Resolved or back to baseline	Resume CFZ at one dose decrement
Pulmonary Hypertension	Grade 3 or 4	Hold CFZ	Resolved or returned to baseline	Resume CFZ at one dose decrement
Pulmonary Complications	Grade 3 or 4	Hold CFZ	Resolved or returned to baseline	Resume CFZ at one dose decrement
Hepatic toxicity	Grade 3 or 4 elevation of transaminases, bilirubin, or other liver abnormalities	Hold CFZ Follow LFT	Resolved or returned to baseline	Resume CFZ at one dose decrement

Carfilzomib for Treatment of cGVHD

*CBC – Frequency of CBC monitoring after holding dose for toxicity is directed by treating clinician's judgment, and not mandated by this protocol. A recommended guideline is weekly until return to baseline.

*LFT – Frequency of LFT monitoring is directed by treating clinician's judgment, in keeping with note above regarding CBC monitoring.

Permissible dose decrements:

- 36mg/m² → 27mg/m²
- 27mg/m² → 20mg/m²
- 20mg/m² → 15mg/m²
- If toxicity persists or reoccurs requiring dose reduction below 15mg/m², then carfilzomib therapy should be discontinued. No more than three dose reductions will be permitted in an individual subject on study. If toxicity continues or recurs after three dose reductions, carfilzomib therapy should be discontinued.
- If toxicity requiring dose reduction occurs on the first dose (i.e. 20mg/m²), only one dose decrement will be possible to 15mg/m². If toxicity persists or recurs on the 15mg/m² dose, carfilzomib therapy should be discontinued.

Conditions not requiring dose reduction:

- Grade 3 nausea, vomiting or diarrhea (unless persisting > 3 days despite treatment with anti-emetics or anti-diarrheals)
- Grade 3 fatigue (unless persisting continuously for >14 days)
- Alopecia
- Hyperglycemia attributed to steroids

Persistent toxicity for 3 weeks after withholding CFZ therapy:

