- If the patient has toxicity attributable to carfilzomib that does not return to baseline or reach < grade 1 in severity by 3 weeks, carfilzomib therapy will be discontinued

Patient tolerates decreased dose following dose reduction for toxicity:

- If the patient tolerates the decreased dose x 2 cycles, full-dose CFZ (i.e. 36mg/m²) should be resumed on subsequent cycles.

- If subsequent toxicity occurs as defined above, the stated rules for dose reduction apply, but a second attempt to resume full-dose therapy should not be made.

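### Section 9.2 tells sites not to record non-serious electrolyte abnormalities or nausea/vomiting, with no exception for grade 3+ events related to carfilzomib, although section 6.2 can hold and reduce the dose for them

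*Combined protocol and SAP*

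**What the plan says.** Section 9.2 opens with a broad rule: "The study will collect all Grade 3 and above adverse events, regardless of relationship to study therapy or study procedures". Grade 1 and 2 events are not collected at all.

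An exception list follows, introduced by "The following are frequent events in the chronic GVHD population and will not be recorded as adverse events", with the single general condition that the event is not serious. Two items matter here:

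- Electrolytes: "Electrolyte abnormalities: Increase or decrease in sodium, potassium, chloride, bicarbonate, phosphorus, magnesium, calcium, hyperglycemia following steroid therapy".
- Gastrointestinal, within a longer list: "difficulty swallowing due to esophageal stricture or narrowing, nausea/vomiting, salivary gland changes".

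Other items are limited by cause. The respiratory item, for example, covers only "shortness of breath, cough, or oxygen requirement associated with pulmonary chronic GVHD involvement".

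Section 6.2 deals with the same kinds of event as toxicity. Its row for other non-hematologic toxicity covers carfilzomib-related events at or above "Grade 3 toxicity not listed individually elsewhere". The action is to hold, then resume at one dose decrement. Electrolytes have no row of their own. Among the conditions that need no reduction, the only metabolic one is "Hyperglycemia attributed to steroids". Grade 3 nausea or vomiting is also there, but only while it has not persisted beyond 3 days despite anti-emetics.

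**The concern.** Because lower grades are never collected, the exception list affects non-serious events only at grade 3 and above. At that level, two items remove events by type without asking what caused them. A site following both sections could hold carfilzomib for a related grade 3 hyponatremia, restart at a lower dose, and correctly leave the event off the adverse-event form.

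The omission would carry forward. Section 9.2 has the DSMB receive, about every 6 months, a compilation of the non-serious events in the database. Section 9.3 puts collected events that are not expedited into the IND annual report. Neither can contain what was not recorded. Appendix B lists no follow-up laboratory item and leaves routine chemistry to institutional practice, so the protocol schedules no laboratory data from which the events could be rebuilt.

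At stake is the completeness of the tolerability data from 20 patients, in a setting where section 10.4 says the drug has not been studied before.

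**Working it through.** The plan states no figure on this point, so there is nothing to reproduce. The check is a comparison of the text, followed by a rough scale.

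**Text, step by step**

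1. Is the electrolyte item limited by grade or cause? Seven analytes are named, in either direction, with no grade. The closing words about steroid therapy most naturally attach to hyperglycemia, which matches the exemption in 6.2. On the wider reading, with the words governing the whole item, there is still no grade limit and nothing that takes out a carfilzomib-related event.
2. Is nausea/vomiting limited? No. Abdominal pain, in the same item, is tied to GVHD; nausea/vomiting is not.
3. Does 6.2 act on these events? For related grade 3+ electrolyte toxicity, yes: hold and one decrement. For grade 3 nausea/vomiting, only after 3 days despite treatment.
4. Does anything restore them to recording? The worsening clause in the first exception concerns abnormalities present at enrollment. Otherwise nothing in 9.1 to 9.6 or Appendix B restores a non-serious event of these types.

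**Scale**

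Inputs: 20 patients (section 3.2); grade 3/4 hyponatremia 8.3% and hypophosphatemia 6.0% among 266 myeloma patients on the 20/27 mg/m² regimen (section 1.2.4), which section 1.3 describes as twice weekly. These are two of the four non-hematologic grade 3/4 events named there.

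- Hyponatremia: 20 × 0.083 = 1.66 patients; chance of at least one = 1 − 0.917^20 = 82%.
- Hypophosphatemia: 20 × 0.060 = 1.20 patients; chance of at least one = 1 − 0.940^20 = 71%.
- Either: between 1.66 patients (full overlap; 82%) and 2.86 (no overlap; 1 − 0.857^20 = 95%).

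Some of these would be serious, and so recorded. The list in 1.2.4 of serious events at 1% or more names neither, so allow up to 1% each:

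- 20 × (0.083 − 0.01) = 1.46 and 20 × (0.060 − 0.01) = 1.00, together 2.46.

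That is the upper end if every event is related to carfilzomib. The lower end is 0 if none is. The documents do not give the related share.

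Two results in section 1.3 point toward the lower part of the range:

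- Once-weekly dosing at 45, 56 and 70 mg/m²: 3 + 3 + 15 = 21 patients, none needing dose reduction for toxicity. The one-sided 95% upper bound is 1 − 0.05^(1/21) = 13%. The upper end above, 2.46/20 = 12%, sits just inside it.
- The 36 mg/m² cohort of the earlier 30-minute-infusion study: no grade 3/4 events, but only 4 patients (upper bound 1 − 0.05^(1/4) = 53%).

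The documents give no overall grade 3 rate for nausea or vomiting, so the range covers electrolytes only.

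**The case against.** The list is a deliberate and sensible choice. Patients with chronic GVHD have many such abnormalities, and recording them all would bury any signal. Serious events are still captured, and 9.1 counts as serious anything life-threatening or requiring hospitalization, and lets judgment add events that jeopardize the patient. What remains is mainly non-serious grade 3 laboratory values and nausea/vomiting. Section 9 also refers to a DSMB Charter and a monitoring plan that are not in hand; these, or the case report forms, may capture dose holds and laboratory values. All of this stands and limits the point. It does not remove the conflict: the stated reason for the list, frequency in this population, is not a test of cause that a site could apply to a related event.

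A reader might infer more than the documents support:

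- *That these events are not adverse events in this trial.* Section 9.1 still defines an abnormal laboratory finding as one; 9.2 only stops it being recorded.
- *That 6.2 reduces the dose for all grade 3 nausea/vomiting.* It does so only when this persists.
- *That 8.3% and 6.0% are drug-related rates.* Section 1.2.4 uses the word related for its any-grade list, not for these figures.
- *That lost dose is part of the harm.* Any reduction follows from 6.2, whether or not the event is recorded.

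**Conclusion.** The point holds and is minor. Followed as written, 9.2 leaves non-serious, carfilzomib-related grade 3+ electrolyte abnormalities and nausea/vomiting out of the adverse-event results, the DSMB compilation and the annual report, although 6.2 may have changed treatment because of them.

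The size is roughly 0 to 2.5 electrolyte records in 20 patients. This assumes that all-cause myeloma rates from a different schedule carry over, that at most 1% of patients have each event in serious form, and that the related share lies anywhere from none to all. The once-weekly data favor the lower part, though only indirectly: they count dose reductions, not grade 3 events, and come from myeloma patients. Any nausea/vomiting events come on top and cannot be sized from the documents.

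The primary endpoint, the non-relapse-mortality stopping rule and the dose actually given do not depend on this.

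**What to change.** Add one sentence after the exception list in 9.2:

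> These exceptions do not apply to Grade 3 or higher events judged related to carfilzomib, or to Grade 3 or higher events for which carfilzomib is held, reduced or discontinued under section 6.2; such events will be recorded.

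Both clauses are confined to grade 3 and above. The collection threshold therefore stays as it is, and lower-grade reasons for a hold, such as grade 2 hypersensitivity or any-grade herpes reactivation, are not drawn in. The exceptions for background chronic GVHD events remain.

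The cost is a few extra entries. No new assessment is needed, because 6.2 already asks the site whether a grade 3+ non-hematologic event is related to carfilzomib. The downside is that attribution is imprecise in a single-arm trial, so some background events will be recorded as related.

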9.3 IND Safety Reporting

An event must meet all three of the following criteria in order to qualify for expedited reporting to the FDA in an IND Safety Report:

- 1) Serious

- 2) Unexpected
- 3) Suspected adverse reaction (i.e. there is a reasonable possibility that the drug caused the event)

The sponsor-investigator is ultimately responsible for determining whether all criteria are met. Details are as follows:

- **Seriousness:** If either the sponsor-investigator or local investigator believes that an event is serious, it must be considered serious and evaluated by the sponsor-investigator for expedited reporting. Similarly, if either the sponsor-investigator or local investigator believes that an event is life threatening, it must be considered life threatening for reporting purposes.
- **Expectedness:** The sponsor-investigator is responsible for determining whether an event is unexpected.
- **Causality:** Although local investigators are required to provide a causality assessment for each serious adverse event originating from their sites, it is ultimately the sponsor-investigator who decides whether the event meets the definition of a suspected adverse reaction.

IND Safety reports will be submitted on a MedWatch3500A form to the FDA and all participating investigators no later than 15 days after the sponsor-investigator determines that the event qualifies for reporting.

Exception: Fatal or life-threatening events will be reported within 7 days of when the sponsor-investigator receives notification of the event.

Relevant additional information should be submitted in a follow-up report as soon as possible, but no later than 15 days after the sponsor-investigator receives the information.

All other adverse events that are collected by the study but do not meet the criteria for expedited reporting will be reported to the FDA in the IND Annual Report.

Notification of SAE that meet requirement for expedited reporting will also be provided to individual site principal investigators of this trial.

9.4 Reporting to Onyx

The coordinating center is responsible for all communication with Onyx. The sponsor-investigator will submit IND Safety Reports (per above guidelines, namely serious, unexpected, suspected adverse reactions) to Onyx in an expedited manner (same criteria

Carfilzomib for Treatment of cGVHD

as above, namely within 24 hours of awareness. This notification will be documented on a MedWatch3500A form.

The initial report will be as complete as possible, at a minimum including the serious adverse event term (s), patient identifier, date of awareness of the event, an assessment of the causal relationship between the event and the investigational product(s), and name of the reporter (investigator). Information not available at the time of the initial report (e.g., an end date for the adverse event or laboratory values received after the report) must be documented on a follow-up MEDWATCH form. The Onyx protocol number and the institutional protocol number will be included on all reports to Onyx.

All other SAEs (i.e. those not meeting above criteria for expedited reporting) will be sent to Onyx within 30 days of awareness, and include the following: Patient identifier, SAE onset and stop dates, event name (term), outcome, dates of study drug exposure, action taken with study drug, assessment of causality and expectedness.

To report a Serious Adverse Event or other safety related information to Onyx Drug Safety please use:

Drug Safety [contact]

Drug Safety [contact] or [contact]

Drug Safety Email: [contact]

9.5 Pregnancy

Female participants of child-bearing potential must have a negative pregnancy test prior to treatment and agree to use dual methods of contraception for the duration of the study and for 30 days following completion of study. Male participants must also agree to use a barrier method of contraception for the duration of the study and for 30 days following completion of study if sexually active with a female of child-bearing potential.

If a subject or partner of a subject becomes pregnant during or up to 30 days following administration of the last dose of carfilzomib, Onyx Drug Safety must be notified by the study-investigator within 24 hours of research personnel becoming aware of it. Carfilzomib must be stopped if a subject becomes pregnant. Subjects or pregnant partners will be followed through the outcome of the pregnancy. The outcome must be reported to Onyx Drug Safety. If the outcome qualifies as a serious adverse event, the serious adverse event reporting procedures should be followed.

9.6 Notifying Institutional Review Boards

Study sites are responsible for adhering to their local IRB guidelines. In general, all investigators are required to promptly report to their IRB *all unanticipated problems involving risk to human subjects or others*. IND Safety Reports, which will be distributed to all investigators, will usually require reporting under this category.

